6.2.2. MDS-UPDRS

Endpoints: MDS-UPDRS Parts I, II, III, IV, and total score

- Analysis time points: All Visits
- Analysis population (method of imputation for missing data): FAS (See [Sections 3.2.1 and 3.2.2](#)).
- Analysis methodology: Change from baseline will be analyzed using the MMRM Analysis (See [Section 5.2.2.1](#)) and Dose Response Analysis (MDS-UPDRS Part III @ Week 10 only, See [Section 5.2.2.2](#)).

- Supporting objective and Decision rule: Secondary Objective (See [Section 2.1.2](#)).

Reporting results:

[figure not shown]
- Raw data: The sample size, mean, standard deviation, median, minimum and maximum at baseline and post-baseline visits will be presented for each treatment arm.
- Change from baseline: The sample size, mean, standard deviation, median, minimum and maximum will be presented for each treatment arm. The point estimate, 90% confidence interval for the point estimate, difference from the placebo for each pair of treatment groups and the corresponding 90% confidence interval will be presented.

Figures

[figure not shown]
- Vertical bar chart of LS means and 90% confidence intervals at Week 10.
- Change from baseline time profile per MMRM for each treatment group.
- Empirical cumulative distribution function showing % of subjects with change from baseline \leq cutoff value at Week 10 by treatment group; (any drop outs are assigned to the left side of x axis).
- Dose response Emax model graph with the MMRM estimates (MDS-UPDRS Part III at Week 10 only).

CCI

CCI

6.4. Subset Analyses

The primary endpoint will also be analyzed respectively for subset of subjects

- in different geographic regions;
- that have or do not have background PD medication changes during Period A; and
- subjects that have <1000 mg/day or \geq 1000 mg/day of L-Dopa intake during baseline.

Only subgroup that has \geq 10% of total subjects will be analyzed. If conducted, the MMRM analysis (See [Section 5.2.2.1](#)) will be performed and similar reporting results as described in [Section 6.1.1](#) will be presented for each of the subset analyses.

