### 3.1.2. Double Blind Period

Eligible subjects will enter the 15 week double blind treatment phase, consisting of:

- Up to 3 week titration of PF-06649751 or placebo administered once daily to the randomized target dose ([Section 5.5.1](#)).
- 2 week stabilization period for dose adjustment after reaching the target dose with possible return to previous dose level after completion of the titration period. For subjects with intolerable adverse events, adjunct L-Dopa dose may subsequently be reduced after consultation with the Medical Monitor (see Section 5.5.1 [Titration of PF-06649751](#)).
- Period A (Primary Efficacy): a 5 week period of PF-06649751 or placebo administered once daily adjunctive to stable doses of L-Dopa ([Section 5.5.2](#)).
- Period B (Maintenance): a 5 week maintenance period of PF-06649751 or placebo administered once daily adjunctive to stable doses of L-Dopa ([Section 5.5.3](#)).

Subjects will return to the clinic at the end of Weeks 1, 2, 3, 4, 5, 10, 15, and 17. Weeks 2 and 3 may be conducted as phone visits, at the discretion of the investigator.

All other visits will be conducted as phone visits; as per Section 6.5 ([Unplanned Visits](#)), the investigator has the discretion to conduct an unplanned clinic visit if warranted for subject safety. For guidance on concomitant medications for Parkinson's disease and other disorders please see Section 5.8, [Concomitant Treatment\(s\)](#).

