5.2.2.1. Mixed Model for Repeated Measures Analysis (Non-Bayesian Approach)

The Mixed Model for Repeated Measures (MMRM) analysis will be based on an analysis of a restricted maximum likelihood (REML)-based mixed model. The response variable will be the change from baseline to each post baseline visit, and the model will include the following fixed effects:

- randomized treatment (with 5 levels: PF-06649751 1 mg QD, 3 mg QD, 7 mg QD, 15 mg QD, and placebo), a categorical factor;
- visit, a categorical factor;
- treatment-by-visit interaction;
- baseline endpoint value, a continuous covariate;
- baseline-by-visit interaction;
- geographic region as appropriate (e.g. North America, Japan, and Europe).

In addition, cohort (Part A, Part B) may also be included as a fixed effect as appropriate.

An unstructured variance-covariance structure will be used to model the within-subject errors. In the unlikely event that the computational algorithm fails to converge, the following structures will be executed in the order specified (essentially in decreasing order of complexity) until convergence is achieved: heterogeneous Toeplitz, heterogeneous first-order

autoregressive, autoregressive, heterogeneous compound symmetry, compound symmetry, and variance components. The first structure yielding convergence will be used as the primary analysis. The Kenward and Roger method⁷ will be used for calculating the denominator degrees of freedom for tests of fixed effects. OM option will be used to derive the least squares means similar to the observed margins. Example SAS code for the MMRM model will be provided in the Programmer's Analysis & Reporting documentation.

The least-squares mean estimates, standard errors, and two-sided 90% CIs for each treatment groups will be reported. The efficacy comparisons based on the treatment difference vs. placebo estimated using least-squares means for each PF-06649751 dose will be conducted, and their point estimates, standard errors, and two-sided 90% CIs will be reported.

The assumptions of normality will be verified graphically using residual plots. For each fitted model, studentized residual plots will be produced. The residual plots will not be included in the clinical study report, but will be sent to the statistician for inspection at the time the analysis is conducted.

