MDS-UPDRS Parts I, II, IV, and total score, All Visits	FAS	MMRM	OC	Secondary Analysis
CCI				
Daily OFF time, Week 10	FAS-North America (Optional*)	MMRM	OC	Subset Analysis

090177e18f6e873a\Approved\Approved On: 26-Sep-2018 05:14 (GMT)

Daily OFF time, Week 10	FAS-EU (Optional*)	MMRM	OC	Subset Analysis
Daily OFF time, Week 10	FAS-Japan (Optional*)	MMRM	OC	Subset Analysis
Daily OFF time, Week 10	FAS-no background PD medication change (Optional*)	MMRM	OC	Subset Analysis
Daily OFF time, Week 10	FAS-background PD medication change (Optional*)	MMRM	OC	Subset Analysis
Daily OFF time, Week 10	FAS-<1000 mg /day and ≥1000 mg/day L-dopa intake (Optional*)	MMRM	OC	Subset Analysis

* Only subgroups that have ≥ 10% of total subjects will be analyzed.

CCI

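### SAP 6.4 compares doses with placebo within subsets defined by medication changes after randomization; if treatment affects who changes, these are not randomized comparisons

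*SAP*

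**What the plan says.** SAP Section 6.4 opens with "The primary endpoint will also be analyzed respectively for subset of subjects" and lists three splits: geographic region, subjects "that have or do not have background PD medication changes during Period A", and L-Dopa intake at baseline below or from 1000 mg/day. Each subset gets the MMRM of Section 5.2.2.1, with "similar reporting results as described in" Section 6.1.1. On the contrasts, Section 5.2.2.1 says: "The efficacy comparisons based on the treatment difference vs. placebo estimated using least-squares means for each PF-06649751 dose will be conducted". They are reported with 90% intervals.

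A subgroup must hold at least "10% of total subjects will be analyzed". SAP Appendix 1 gives each half of the medication split its own row, marked optional: "FAS-no background PD medication change (Optional" and "FAS-background PD medication change (Optional".

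Protocol Section 3.1.2 sets the timing: "Period A (Primary Efficacy): a 5 week period of PF-06649751 or placebo administered once daily". It comes after up to three weeks of titration and two weeks of dose adjustment.

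Section 6.4 does not define a background PD medication change. SAP Section 6.5.4 counts such changes in Period A and Period B and leaves L-Dopa out of the count. Neither 6.4 nor Appendix 1 limits how the subset results may be read.

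**The concern.** Region and baseline L-Dopa intake are fixed before treatment, so each of their subsets still compares randomized groups. Whether a subject changes co-medication in Period A is settled only after five weeks on blinded treatment and may depend on it. A subject who responds poorly has a reason to add something, and a subject with side effects has a reason to cut back. If the drug alters either reason, the subjects left in the 'no change' half of the placebo arm differ in kind from those left in the active arms, and their difference mixes drug effect with selection.

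The 'no change' half matters more. It will almost certainly pass the 10% condition, and it invites reading as the drug effect with co-medication held stable. It does not estimate that when treatment affects who changes.

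**Working it through.** **Inputs.** From Protocol Section 9.1: SD 2.9 h for the change in daily OFF time, 32 evaluable subjects per arm, target effect 2.25 h, C1 threshold 1.5 h. Assumed, because the documents are silent: placebo change rate p = 10%, 20% or 30%, and correlation r = 0.3, 0.5 or 0.7 between OFF-time response and the tendency to change medication. A positive difference is a benefit of the drug.

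**Plan's own figures.** SE = 2.9 × √(2/32) = 0.725 h. C2 needs 1.645 × 0.725 = 1.19 h, so the 1.5 h of C1 is the binding criterion. P(pass | 2.25 h) = Φ((2.25 − 1.5)/0.725) = 0.850 and P(pass | 0) = 1 − Φ(1.5/0.725) = 0.019. The protocol states 85% and 2%, so both reproduce.

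**Model.** Subjects in both arms follow the same rule: the worse the response, the likelier a change. On placebo the rule is a normal threshold z with 1 − Φ(z) = p. A true effect of 2.25 h is 2.25/2.9 = 0.776 SD, so on active drug the threshold becomes z′ = z + 0.776r, with change rate p′ = 1 − Φ(z′). Leaving out the changers improves the mean response of those who remain by 2.9 × r × φ(z)/(1 − p) on placebo and 2.9 × r × φ(z′)/(1 − p′) on active. The 'no change' difference is 2.25 minus the excess of the placebo shift over the active shift.

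**One cell in full (p = 20%, r = 0.5).**
- Placebo: z = 0.842, φ(z) = 0.280, shift = 1.45 × 0.280/0.80 = 0.507 h.
- Active: z′ = 0.842 + 0.388 = 1.230, p′ = 10.9%, φ(z′) = 0.187, shift = 1.45 × 0.187/0.891 = 0.305 h.
- 'No change' difference: 2.25 − (0.507 − 0.305) = 2.05 h.

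**All nine cells, 'no change' difference in hours (true effect 2.25 h).**

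| r | p = 10% | p = 20% | p = 30% |
|---|---|---|---|
| 0.3 | 2.20 | 2.17 | 2.15 |
| 0.5 | 2.12 | 2.05 | 2.00 |
| 0.7 | 2.01 | 1.88 | 1.78 |

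Simulation of the same model agrees to within 0.01 h. Its 'change' half shows 1.3 to 2.1 h.

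**Rare changes (p = 5%, r = 0.5).** The shifts are 1.45 × 0.103/0.95 = 0.157 h on placebo and 1.45 × 0.0505/0.979 = 0.075 h on active (z′ = 2.033, p′ = 2.1%). The difference is 2.25 − 0.08 = 2.17 h.

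**No effect of the drug on who changes.** Under the same rule with a true effect of 0, z′ = z, the shifts cancel, and the difference is 0 for any p and r.

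**The 'change' half at the size condition.** 10% of 198 is about 20 subjects, or about 4 per arm if spread evenly: SE = 2.9 × √(2/4) = 2.05 h, and the 90% half-width is 1.645 × 2.05 = 3.4 h. It would be too imprecise to inform anything.

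**Replacement analysis.** SAP Section 3.1 places the post-baseline diaries at Weeks 3, 5 and 10 up to the end of Period A. A Period A change therefore removes the Week 10 value itself, and the MMRM recovers only what earlier diaries predict. With a Week 5 to Week 10 correlation c, the bias left is roughly (1 − c²) of the subset bias when change follows the Week 10 state. In the worked cell, 0.20 h falls to about 0.15 h (c = 0.5) or 0.10 h (c = 0.7). Simulation over assumed rates and correlations gave 1.77-2.23 h for the 'no change' subset and 1.86-2.26 h for the MMRM in all FAS subjects, which was about 2.25 h when change follows the Week 5 response.

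**The case against.** The strongest counter-case is that changes should be rare and the consequence small. Protocol Section 5.8.1 asks for stable doses of MAO-B and COMT inhibitors, amantadine and anticholinergics through the double-blind period. The documented routes by which treatment could cause a change, reduction for dopaminergic side effects and rescue, both concern L-Dopa, which SAP 6.5.4 excludes. Rescue days have their own rule in SAP 3.1. On that reading the 'change' half may miss the 10% condition and the 'no change' half would be close to the FAS. This stands, and it bounds the size. It does not settle the point, because 6.4 does not say that L-Dopa is excluded and the 'no change' contrast is produced in either case.

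A reader might infer that the contrast is biased even when the drug does nothing. For example, if 20% of placebo and 5% of active subjects changed because of poor response to an inert drug, the formula would give 2.9 × (0.350 − 0.109) = 0.70 h at a correlation of 1.0, 0.35 h at 0.5 and 0.21 h at 0.3. The documents do not support this. In a randomized, blinded trial an inert drug leaves the same responses in both arms, so response-driven changes occur at equal rates and the bias is zero. Those rates appear nowhere in the plan, and even in that example the error runs against the drug.

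A reader might also infer a false benefit in the 'change' half. That requires reasons for change that differ by arm, for which the documents give no evidence outside L-Dopa.

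It is also fair that the replacement is imperfect, and that 6.5.4 already plans the descriptive count.

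**Conclusion.** The point holds in limited form. Section 6.4 conditions a dose-versus-placebo comparison on a post-randomization variable. Such a contrast is protected by randomization only if treatment does not affect who changes, and the plan neither assumes nor limits this. Under the stated assumptions the 'no change' half shows about 1.8-2.2 h for a true 2.25 h, so it understates the drug when poor responders change. With rare changes the error is about 0.1 h or less at a correlation of 0.5. Direction and size depend on why subjects change, which the documents do not tell us.

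A reader should not infer that the trial's conclusion is at risk. The analysis is optional and size-limited. It feeds neither C1 and C2 nor the primary FAS analysis. Severity is low.

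**What to change.** - Remove the medication-change split from SAP 6.4 and its two rows from Appendix 1.
- Define a background PD medication change once, consistently with 6.5.4, and state whether L-Dopa counts.
- Add a sensitivity MMRM for Week 10 that keeps every FAS subject in the randomized arm and sets diary values after the change to missing. State that it assumes missing at random, and that bias is reduced rather than removed because only the Week 3 and Week 5 diaries remain after a Period A change.
- Show the 6.5.4 change counts by arm, so that a reader can see whether changes differ between arms at all.

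The cost is SAP wording and one optional analysis exchanged for another of similar size. The downside is that the new analysis rests on missing at random. No sample size, data collection or primary analysis changes.

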6.5. Baseline and Other Summaries and Analyses

6.5.1. Study Conduct and Subject Disposition

Data will be reported in accordance with Pfizer Data Standards. Disposition will be further categorized by the treatment phase Titration, Dose Adjustment, Period A, Period B (may be separated by preA2 and A2), and Follow-up.

Overall subject disposition will include data through Double-Blind treatment period (study treatment period) and separately through Follow-up (overall study).

The number of subjects by region and country will be displayed.

6.5.2. Baseline Summaries

A breakdown of demographic data will be provided for age, race, weight, body mass index, height, and temperature. Each parameter will be summarized with tables and listings presented in accordance with the Pfizer Data Standards. Use geriatric age categories for the demographic summaries (<65, 65-74, 75-84, and ≥85). Physical measurements at Baseline will include weight, height, BMI, and temperature.

Also, medical history and primary diagnosis will be tabulated and listed in accordance with the Pfizer Data Standards.

Females of childbearing potential are excluded from the study. All female subjects of non-childbearing potential will have a FSH test, if amenorrheic for at least 12 consecutive months. Results will be obtained prior to PF-06649751 or placebo dosing. Information will be captured in the listings only.

The following baseline characteristics will be summarized:

- Hauser home diary endpoints (OFF time + all other diary measures) (continuous data);
- CCI [REDACTED]
- QUIP-RS;
- MMSE Total Score (continuous data);
- Hoehn & Yahr Stage while the subject is ON (categorical data);
- MDS-UPDRS Part I, II, III, IV, and Total Score at Baseline (continuous data);
- Prescribed L-Dopa dose (continuous data);
- Number of Background concomitant Parkinson's Disease medications @ Randomization (categorical);
- Region (categorical).

6.5.3. Study Treatment Exposure

Duration of exposure will be presented in tables and listings in accordance with the Pfizer Data Standards.

Compliance will be calculated and summarized across the whole double-blind treatment phase, and by visit. Compliance will be based on the dosing record, and calculated as:

$$\% \text{Compliance} = 100 \times (\text{Actual \# of Capsules Taken}) / (\text{Total \# Capsules Prescribed})$$

Subjects who fail to return blister information will be considered missing for that visit.

6.5.4. Concomitant Medications and Non-Drug Treatments

All prior and concomitant medication(s) as well as non-drug treatment(s) will be provided in tables and listings in accordance with the Pfizer Data Standards. Concomitant Parkinson's Disease medication(s) use will also be summarized by treatment group.

Frequency and type of medication will be summarized categorically by treatment group. Descriptive statistics of doses of background antipsychotic medication will also be summarized.

The number of rescue medication doses used for subjects will be presented by treatment group overall and by visit (summarized as continuous data).

The number and percentage of subjects with a change in their background PD medications (excluding L-Dopa) for Period A and Period B (summarized as categorical data).

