#### 3.1. Study Overview

The study has a randomized, double-blind, placebo-controlled parallel group design. Approximately 198 subjects from approximately 60 centers in approximately 6 countries will be randomized to 5 treatment groups (15 mg QD, 7 mg QD, 3 mg QD, 1 mg QD, or placebo), initially in a 2:0:0:0:1 ratio of approximately 54 subjects (Cohort 1) followed by a 1:2:2:2:1 ratio of approximately 144 subjects (Cohort 2), using a central randomization system with randomization blocks stratified by region.

Each subject will participate in the study for approximately 25 weeks including up to a 45 day screening period, 15 week double-blind treatment period (comprising up to a 3 week titration, 2 week dose adjustment, 5 weeks of primary efficacy with adjunctive treatment to stable L-Dopa (Period A), and 5 weeks of maintenance with adjunctive treatment to stable L-Dopa (Period B)), and an approximately 28 day follow-up period.

The study design is illustrated in the figure below. For details on the dosing during the titration phase, see Section 5.5.1, **Titration of PF-06649751**.

Figure 1. Study Schematic

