**Table 2. Proposed Titration Schemes for PF-06649751 and Placebo Doses**

Week/ Start Day of Dose Level	Treatment Group				
	Placebo	1 mg	3 mg	7 mg	15 mg
Week 1 / from Day 1	P	1 mg	1 mg	1 mg	1 mg
Week 2/ from Day 8	P	1 mg	3 mg	3 mg	3 mg
Week 3 / from Day 15	P	1 mg	3 mg	7 mg	7 mg
Weeks 4-15 / from Day 22	P	1 mg	3 mg	7 mg	15 mg

**Titration (Week 1 to Week 3):** No modifications to the upward titration of Study Medication can be made. Subjects who experience intolerable adverse events during titration will need to be discontinued from the study.

**Post Week 3 (Week 4 to Week 5):** For subjects who experience unacceptable new adverse events after having achieved the target dose (after Day 21) and deemed related to the dose increase, the dose of investigational product can be changed to the previous dose level (Week 3 dose level). This results in a dose reduction from 15 mg/day to 7 mg/day for the highest dose group, and no change in dose for the other dose groups in a blinded fashion. Only one dose modification of investigational product is permitted.

**L-Dopa Adjustment for Unacceptable Dopaminergic Side Effects (Week 1 to Week 15):** In the case of unacceptable dopaminergic side effects and following discussion with the Medical Monitor, the dose of L-Dopa may be reduced between Day 1 and Day 105 visit.

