### **5.8. Concomitant Treatment(s)**

Subjects will abstain from all concomitant medications as outlined in [Appendix 3](#) and [Appendix 4](#) except for:

- The treatment of adverse events.
- [Rescue Medication](#), as described in Section 5.9.
- All concomitant medications taken during the study must be recorded with indication, daily dose, and start and stop dates of administration. All subjects will be questioned about concomitant medication at each clinic and telephone visit.

Medications taken within 60 days before the first dose of study investigational product will be documented as a prior medication. Medications taken after the first dose of study investigational product will be documented as concomitant medications.

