### **5.9. Rescue Medication**

Rescue medication is permitted in the form of L-Dopa. The dose and dose frequency can be defined using investigator discretion based on patients' needs. Rescue L-Dopa may be administered if needed in between study visits based on a phone consultation and the discretion of the investigator.

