#### **9.1. Sample Size Determination**

The sample size is based on a pair-wise comparison of a dose of the PF-06649751 against placebo and is based on the primary endpoint, the change from Baseline to Week 10 (end of Period A) in the daily OFF time. The decision criteria for efficacy are given as below, which will be based on a Bayesian interpretation of the results:

- C1: Point estimate of PF-06649751 vs. placebo effect  $\geq 1.5$  hours, and
- C2: 95% confident of PF-06649751 vs. placebo effect  $\geq 0$ .

Better is defined as a reduction in the daily OFF time.

The sample size indicates that 32 evaluable subjects per arm will give sufficient precision for a comparison of an active dose versus placebo to meet criterion C2 with observed effects of  $\geq 1.5$  hours (Criterion C1). It's estimated that the probability of passing both criteria for a true effect of 2.25 hours would be 85%, and the probability of passing the criteria for a true null effect (0 hour) would be 2%.

Accounting for a 10% rate of non-evaluable subjects as well as dropouts before the stable dose period (ie, by 5 weeks post dose), 36 subjects per arm and an approximate total of

198 subjects (54 in Cohort 1 and 144 in Cohort 2) are expected to be randomized for the study. Depending on actual enrollment, additional subjects may be randomized in the same treatment ratio, but there will be no more than 260 subjects in total.

The calculations were based on an estimate of the variability obtained from a meta-analysis of the historical Parkinson's disease trials. This provided an estimate of the between subject standard deviation of 2.9 hours in change from baseline in daily OFF time. The meta-analysis also provided an informative prior for placebo effect, which will be included in the Bayesian data analysis.

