7. The daily OFF time for every rescue diary day will be replaced by the subject's baseline OFF time, that is, the baseline 3-day average. (All periods through Period A, and additionally Period B for subjects consented under Protocol Amendment 2 prior to entering Period B).

Daily Average (Rescue diary days are for all periods through Period A, and additionally Period B for subjects consented under Protocol Amendment 2 prior to entering Period B)

8. Valid home diary days (at least 12 awake hours, after all imputation) and/or rescue diary days will be used to compute the average daily OFF time. The valid home or rescue diary day must be within 7 days of the clinic visit (or phone visit for Week 3 only as noted below or assigned to the closest planned visit as noted below) but not on or after the day of the clinic visit. If more than 3 valid home or rescue diary days are available, the 3 days closest to the clinic visit will be used.
 - Prior to Protocol Amendment 2, the three consecutive days before Day 0 could occur anytime during the screening period and was not restricted to within a week of the visit. Therefore, all home diaries before Day 0 will be considered for Baseline, with the 3 days closest to Day 0 being used for analysis.
 - Subjects, who have a phone visit for Week 3 and their home diary collected at Week 4, will use their Week 3 phone visit to determine within 7 days.
 - If a valid home or rescue diary is considered for exclusion based on the "within 7 days" rule, it will still be included if its nominal visit is equal to the closest planned visit, otherwise it will be excluded. Planned visits: Baseline (Day -1), Week 3 (Day 21), Week 5 (Day 35) or Week 10 (Day 70).
 - i. Example 1: A subject who completed Week 3 diaries on Days 8, 9, and 10 with the actual Week 3 visit occurring on Day 21. All diaries excluded as all Week 3 diaries would all have been closer to Baseline (Day -1) than Week 3 (Day 21).

- ii. Example 2: A subject who completed Week 10 diaries on Days 61, 62 and 63 with the actual Week 10 visit occurring on Day 70. All diaries included because the diaries are closest to Day 70 which matches the clinic visit (Week 10).
 - iii. Example 3: A subject who completed their Week 3 diaries on Days 11, 12 and 13 but the actual Day 21 visit occurred on Day 24. All diaries included because the diaries are closest to Day 21 which matches the clinic visit (Week 3).

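### The overall rescue L-Dopa summary in SAP 6.5.4 is a raw dose count with no adjustment for time observed, so an arm with more early loss would show a lower mean at the same weekly use

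*SAP*

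**What the plan says.** SAP 6.5.4 states: "The number of rescue medication doses used for subjects will be presented by treatment group overall and by visit (summarized as continuous data". Paired with the by-visit rows, the overall figure reads as the total over a subject's time in the study. The section gives no rate, no rule for subjects who leave early, and no definition of the interval behind a visit row. It specifies no test, contrast or model for rescue.

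Other parts of the plan bear on this:

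- Rescue is open-ended. Protocol 5.9: "Rescue L-Dopa may be administered if needed in between study visits based on a phone consultation and the discretion of the investigator".
- Use is picked up by asking. Protocol 5.8: "All subjects will be questioned about concomitant medication at each clinic and telephone visit".
- A completer is followed through a "15 week double-blind treatment period" (Protocol 3.1).
- Protocol 5.5.1 allows no change to the upward titration: "Subjects who experience intolerable adverse events during titration will need to be discontinued from the study".
- Time on drug is reported in a separate table. SAP 6.5.3: "Duration of exposure will be presented in tables and listings in accordance with the Pfizer Data Standards". It is not linked to the rescue count.
- Rescue reaches the primary endpoint by another route. SAP 3.1: "The daily OFF time for every rescue diary day will be replaced by" the subject's baseline three-day average.

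**The concern.** A total number of doses grows with time observed. A subject who leaves at Week 3 has three weeks in which rescue can be recorded; a completer has fifteen. Averaging the two within an arm mixes rescue use with retention.

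Unequal retention is plausible here. Intolerance during Weeks 1-3 leads to discontinuation, and only the higher-dose arms step up through that period. An arm that is harder to tolerate could therefore show a lower mean rescue count simply because its subjects were observed for less time.

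The stake is one of interpretation. Because rescue diary days are overwritten with baseline OFF time, readers will want to know how much rescue each arm used, and this is the table they will turn to.

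**Working it through.** **Plan figures.** The documents state no rescue rate and no dropout by arm, so there is no rescue figure to reproduce. The one loss figure is in Protocol 9.1: "Accounting for a 10% rate of non-evaluable subjects as well as dropouts before the stable dose period". It reproduces the planned arm size: 32 / 0.90 = 35.6, rounded up to 36. It is a single allowance for all arms and includes non-evaluable subjects. Below, 10% serves only as an assumed comparator value.

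**Overall row.** Inputs:

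- follow-up of a completer: 15 weeks (Protocol 3.1)
- d = share leaving early (assumed)
- w = week of leaving (assumed 1, 3 or 5)
- r = weekly rescue rate, the same in both arms (assumed 1 dose per week; it cancels in the ratio)

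Mean count per subject = r x [15(1 - d) + w x d]. At w = 3:

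- d = 10%: 13.5 + 0.3 = 13.8
- d = 20%: 12.0 + 0.6 = 12.6
- d = 30%: 10.5 + 0.9 = 11.4
- d = 40%: 9.0 + 1.2 = 10.2

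Mean counts, with the ratio to the 10% arm in brackets:

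| Week of leaving | 10% loss | 20% loss | 30% loss | 40% loss |
|---|---|---|---|---|
| 1 | 13.6 | 12.2 (0.90) | 10.8 (0.79) | 9.4 (0.69) |
| 3 | 13.8 | 12.6 (0.91) | 11.4 (0.83) | 10.2 (0.74) |
| 5 | 14.0 | 13.0 (0.93) | 12.0 (0.86) | 11.0 (0.79) |

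The shortfall runs from 1 - 0.93 = 7% to 1 - 0.69 = 31% with no true difference. Put the other way, at 30% against 10% and Week 3, a true weekly rate 13.8 / 11.4 = 1.21 times as high would give equal means. With equal loss the ratio is 1.00. Dividing total doses by total person-weeks returns r in both arms, ratio 1.00.

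**By-visit rows.** Contacts with a concomitant-medication check under the current Schedule of Activities fall at Weeks 1, 2, 3, 4, 5, 6, 8, 10, 13 and 15. The gaps are 7 days up to Week 6, then 14, 14, 21 and 14 days.

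- If a row counts doses since the previous contact among subjects still observed, its mean is r x interval in both arms, so the between-arm ratio is 1.00.
- If leavers stayed in the denominator as zeros, the artefact would return. After a Week 3 exit, 30% against 10% loss gives 0.70 / 0.90 = 0.78.
- At a constant 1 dose per week, a 7-day row shows 1, a 14-day row 2 and a 21-day row 3. Undivided rows therefore cannot be read as a time trend.

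The SAP does not say which denominator or interval applies.

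**The case against.** The strongest reply is that this is one supportive table. The SAP only presents the count, and criteria C1 and C2 (SAP 5.1.2) do not use it. Disposition by treatment phase (SAP 6.5.1) and duration of exposure (SAP 6.5.3) are reported, so unequal follow-up will be visible. The by-visit rows are already planned, and the Week 10 row lies closer to the primary endpoint than any 15-week figure. All of this stands and keeps the point minor. It does not make the overall row interpretable on its own.

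A reader might infer stronger versions that the documents do not support:

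- **That 15 mg will lose about 24% against 10% on placebo.** The first figure would be the 11 discontinuations for adverse events among 45 subjects in B7601005 (Protocol 1.4.2). That count pools cohorts at 5 mg (9), 15 mg (11), 15 mg with dyskinesia (6) and 25 mg (19) in an open-label study, with no split by dose. The 10% is an all-arm planning allowance, not a placebo rate.
- **That visit rows span up to 35 days, from Week 5 to Week 10.** This overlooks the Week 6 and Week 8 phone visits, where concomitant medication is assessed. The longest scheduled gap is 21 days. The intervals are also common to all arms, so they do not bias a between-arm reading at a given visit.
- **That the count distorts the efficacy result.** Rescue affects the primary endpoint only through the replacement of rescue diary days.

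**Conclusion.** The point holds for the overall row: a raw count with no time denominator is lower in an arm with more early loss, at equal weekly use. On purely assumed inputs (20-40% loss against 10%, at Weeks 1-5, constant and equal weekly rate) the shortfall is about 7-31%. With equal loss it is zero.

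The by-visit rows largely avoid the problem for between-arm reading, provided they rest on subjects still observed. What is missing there is the statement of denominator and interval.

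The direction is conditional. If the subjects who leave are heavy rescue users, a simple rate is affected too and does not correct for that selection. The consequence is limited to the reading of a descriptive table.

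**What to change.** In SAP 6.5.4:

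- Report overall rescue use by arm as doses per subject-week on treatment (total doses / total person-weeks, both over the same window), beside the raw count.
- Base each by-visit row on subjects still observed, show that number, and divide by days since the previous scheduled contact, clinic or phone.
- Add a footnote that the rate does not adjust for selective loss of heavy rescue users.

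The cost is SAP wording and one derived variable from data already collected. Trial conduct and the primary analysis do not change.
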